### 12.6.3.10 BoExp in Subjects Quitting Smoking

The data to be followed for subjects who quit smoking are:

CO (ppm) in exhaled breath, COHb in blood (%), Urinary BoExp and NEQ (expressed as quantity excreted and concentration adjusted for creatinine) in 24 hour urine collection, hs-CRP, homocysteine, blood glucose, LDL, HDL, TG, TC, fibrinogen, HbA1c, sICAM-1, total white blood cell count, platelet count, 8-epi-PGF2 $\alpha$  and 11-DTX-B2.

These data will be plotted and summarized versus time since quitting for all subjects who quit smoking. The time since quitting will be rounded up to the nearest 30 days, such that a subject who quits before the Day 30 Visit will be assumed to have quit smoking for 30 days at the Day 30 Visit, 60 days at the Day 60 Visit and 90 days at the Day 90 Visit. Similarly a subject who quits smoking between the Day 30 Visit and the Day 60 Visit will be assumed to have quit smoking for 30 days at the Day 60 Visit and 60 days at the Day 90 Visit, and a subject who quits smoking between the Day 60 Visit and the Day 90 Visit will be assumed to have quit smoking for 30 days at the Day 90 Visit.

The data will be presented in the below outputs if more than 5 subjects quit smoking in the THS 2.2 Menthol or MCC arm in a separate Appendix of the CSR.

TFL number	Title
FIGURES	
15.1.2.29	Biomarkers of Exposure and Risk Markers in Subjects who Quit Smoking vs. Time Since Quitting Smoking Arithmetic Mean and 95% CI – Subjects Quitting THS and CC
TABLES	
15.2.4.69	Descriptive Statistics of Biomarkers of Exposure and Risk Markers in Subjects who Quit Smoking Summarized by Time Since Quitting Smoking – Subjects Quitting THS and CC

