3.3 Exploratory Objectives

The exploratory objectives of this study are:

- To describe the following parameters in a confinement and/or ambulatory setting in smokers switching from mCC to THS 2.2 Menthol as compared to smokers continuing to smoke mCC and to SA:
 - Excretion of mutagenic material in urine.
 - Subjective effect of smoking.
 - Cytochrome P450 2A6 (CYP2A6) activity.
- To describe the following parameters over the course of the study in smokers switching from mCC to THS 2.2 Menthol as compared to smokers continuing to smoke mCC:
 - Product evaluation.
 - Smoking puffing behavior.
- To describe the following parameter over the course of the study in smokers switching from mCC to THS 2.2 Menthol:
 - Potential combustion occurrences in tobacco plugs.
- To describe the changes in levels of oxysterols on Day 6 and Day 90 Visit in smokers switching from mCC to THS 2.2 Menthol, and in smokers switching from mCC to SA.
- To describe the product use over the course of the study according to the product preference of the subject.
- To describe the smokers' mental state for the intention to quit at Screening, on Day -2, Day 30 Visit, Day 60 Visit, and Day 90 Visit.
- To describe the changes and reductions in the levels of urinary BoExp and risk markers measured in 4-hour urine fraction on Day 90 Visit in smokers switching from mCC to THS 2.2 Menthol as compared to smokers continuing to smoke mCC and to SA.
- To evaluate in smokers switching from mCC to THS 2.2 Menthol, and smokers continuing smoking mCC the relationship between¹ :
 - Primary and secondary BoExp and nicotine equivalents (NEQ).

- To determine the concordance between the results for BoExp and risk markers in 24-hour urine and in 4-hour urine fraction ².
- To monitor the BoExp in subjects quitting smoking according to the time since they quitted ².

¹ The reporting of the objective will be the subject of a separate report.

² The reporting of the objective will be the subject of an appendix to the main Clinical Study Report.

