- They are several-fold higher in smokers than in smokers abstinent from smoking (Lindner et al., 2011).
- They exhibit, on average, an elimination half-life of \leq 24 hours. Therefore, the 5 days of exposure are sufficient to reach the maximum reduced levels with the THS 2.2 Menthol and SA arms (4 to 5 times the half-life will lead to less than 5% of the original exposure levels of assessed biomarkers on Day 5).

Total NNAL was selected as primary endpoints at Day 90 Visit of THS 2.2 Menthol use as:

- This biomarker is tobacco specific (Goniewicz et al., 2009), and exhibits, on average, an elimination half-life of 10 to 15 days. Therefore, the 91 days of exposure are sufficient to reach the steady state with the THS 2.2 Menthol and SA arms (4 to 5 times the half-life will lead to less than 5% of the original exposure levels on Day 90 Visit).

Some risk markers have been selected in order to evaluate biological changes in THS 2.2 Menthol arm as compared to mCC arm using SA arm as a reference point to verify if the trend of changes upon THS 2.2 Menthol use follow the same trajectory as SA. Among the ones selected, some are well-known to be affected by smoking and to be reversible upon SA as follows:

- CYP1A2 activity, the enzyme which mainly metabolizes caffeine, is decreased as soon as 5 days of SA and after 5 days of use of another candidate MRTP (Faber et al., 2004) and data on file from a previous study (YVD-CS01-EU study).
- 11-DTX-B2 (a major stable metabolite of thromboxane A2, which elicits mainly platelet aggregation) was decreased after 1 week of SA (Benowitz et al., 1993) and after 5 days of use of another candidate MRTP (YVD-CS01-EU study).
- Blood pressure, hs-CRP, fibrinogen, homocysteine, fasting blood glucose, LDL, HDL, TG, TC, hemoglobin A1c (HbA1c), waist circumference, sICAM-1, WBC count, Apo A1, Apo B, and 8-epi-PGF2 α will be evaluated as risk markers (Eliasson et al., 2001; Vasan et al., 2006) for cardiovascular monitoring purposes. According to the literature, some of these risk markers are known to be sensitive to smoking cessation: the levels of HDL increase when the levels of sICAM-1, WBC count, and 8-epi-PGF2 α decrease following 1 to 3 months of smoking cessation (Pilz et al., 2000; Eliasson et al., 2001).

- Body weight as a mean increase of 4.5 kg is observed after 12 months of smoking abstinence with the most weight gain occurring within the first 3 months of quitting (Aubin et al., 2012).

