7.8 Other Study Procedures

7.8.1 Product Use Electronic Diary

A product use electronic diary will be used for the documentation of used Menthol Tobacco Sticks, smoked CCs (menthol and non-menthol), used NRTs product, or the use of other nicotine/tobacco containing products. All subjects (including those subjects randomized to the SA arm) must complete this diary on a daily basis from the time of Discharge on Day 6 until the time of Discharge on Day 90 Visit (Day 91). Subjects will be trained by site staff in the use of this electronic diary during the confinement period at the time the diary is delivered to the subject.

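### SAP 12.6.3.10 labels everyone who quits between two visits as 30 days quit at the next visit, which overstates time since quitting and makes slowly cleared markers such as Total NNAL look slower to clear than they are

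*SAP*

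**What the plan says.** Protocol 3.3 sets the exploratory objective: "To monitor the BoExp in subjects quitting smoking according to the time since they quitted". It mentions no rounding. SAP 12.6.3.10 implements it: "These data will be plotted and summarized versus time since quitting for all subjects who quit smoking". The outputs are Figure 15.1.2.29 (arithmetic mean with 95% CI) and Table 15.2.4.69.

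The same section then coarsens the time variable: "The time since quitting will be rounded up to the nearest 30 days". Its worked cases show what is meant. In the first interval, "a subject who quits before the Day 30 Visit will be assumed to have quit smoking for 30 days at the Day 30 Visit", with 60 and 90 days assigned at the two later visits. A subject who quits between the Day 60 and Day 90 Visits "will be assumed to have quit smoking for 30 days at the Day 90 Visit". No reason is given for the rule.

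The outputs appear "if more than 5 subjects quit smoking in the THS 2.2 Menthol or MCC arm in a separate Appendix of the CSR".

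Finer timing data are collected anyway. Under Protocol 7.8.1, subjects in all arms "must complete this diary on a daily basis from the time of Discharge on Day 6", up to discharge on Day 91, covering every nicotine or tobacco product. Use during confinement is logged by site staff (Protocol 6.5.2.1).

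**The concern.** Time since quitting is the one explanatory variable the objective names. The rule sets it to the upper end of each 30-day step, so the error runs one way: time is overstated, almost never understated. Subjects one day after their last cigarette and subjects four weeks after it share a point plotted at 30 days.

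For a marker that clears over weeks, the mean at that point is well above the level of someone who really has been abstinent for 30 days. A reader of the appendix would conclude that the marker clears more slowly than it does, and more slowly than the protocol's own half-life implies.

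**Working it through.** **Inputs**
- Rounding rule and worked cases: SAP 12.6.3.10.
- Nominal visit days 30, 60 and 90, with a window of ±5 days: Protocol 9.3.
- Total NNAL: "elimination half-life of 10 to 15 days" (Protocol 4.2).
- The four Day 5 primary biomarkers: average half-life of 24 hours or less (Protocol 4.2).

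**Step 1: reproduce the rule.** With quit day Q and visit day V, assigned time = 30 × ceil((V − Q)/30).
- Q = 6: V = 30 gives 24 → 30; V = 60 gives 54 → 60; V = 90 gives 84 → 90.
- Q = 31, V = 60: 29 → 30.
- Q = 61, V = 90: 29 → 30.

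These match the SAP's worked cases.

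**Step 2: actual time behind each label (nominal visit days)**

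| Quit day | Visit | Label (days) | Actual days |
|---|---|---|---|
| 6–29 | Day 30 | 30 | 1–24 |
| 6–29 | Day 60 | 60 | 31–54 |
| 6–29 | Day 90 | 90 | 61–84 |
| 31–59 | Day 60 | 30 | 1–29 |
| 61–89 | Day 90 | 30 | 1–29 |

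A quit on Day 1, in confinement, gives 29 days at the Day 30 Visit. A quit on Day 30 or Day 60 itself gives exactly 30 days at the next visit. With quit days spread evenly (assumption), the mean actual time at the next visit is (1 + 24)/2 = 12.5 days in the first interval and (1 + 29)/2 = 15 days in the later ones, against the label of 30.

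**Step 3: effect on Total NNAL.** Fraction remaining = 2^(−t/h). This assumes first-order elimination, a steady level before quitting and full abstinence afterwards. The steady-level assumption suits a quitter from the mCC arm better than one from the THS arm, whose NNAL may still be falling after the switch.

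| Time since quitting | h = 10 days | h = 15 days |
|---|---|---|
| 1 day | 93.3% | 95.5% |
| 30 days (true) | 12.5% | 25.0% |
| Mean over 1–29 days | 41.6% | 53.8% |

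The last row is (1/29) × r(1 − r^29)/(1 − r), with r = 2^(−1/h):
- h = 10: r = 0.9330, r^29 = 0.1340, sum 12.07, mean 0.416.
- h = 15: r = 0.9548, r^29 = 0.2618, sum 15.61, mean 0.538.

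The later labels are off too. A quit on Day 29 has 31 actual days at the Day 60 Visit (11.7% to 23.9% remaining) but is plotted at 60 days, where 1.6% to 6.3% would remain.

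**Step 4: effect on fast markers.** At a 24-hour half-life, the mean of 2^(−t) over t = 1 to 29 is about 1/29, or 3%, against essentially zero at 30 days. Only very recent quitters matter.

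**Step 5: visit windows.** A quit on Day 31 with a visit on Day 65 is 34 days. Rounding up gives 60; the worked case for that interval gives 30. The two statements of the rule can disagree, so two programmers could produce different tables.

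**The case against.** The strongest defence is that this is ordinary 30-day binning labelled by the upper limit. Actual-day bins of 1–30, 31–60 and 61–90 days would hold the same subjects apart from visit-window cases, so only the label would change. Finer bins would be harmful: the outputs can be triggered by as few as six quitters, and SAP 12.1.5.1 suppresses summaries for categories with fewer than 4 subjects. This stands as an argument for keeping broad bins in the table. It does not defend plotting a group at 30 days when its members average about half that.

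Four stronger readings are tempting, and the documents do not support them.
- A reader might infer that the diary supplies the quit date. It records daily use and has no quit-date field. SAP 12.6.3.10 does not define a quitter, a lapse or the handling of diary gaps. SAP 12.1.5 treats missing use as baseline cigarette use when diary data are sparse, which could move a derived date.
- A reader might infer that the decline of every marker is flattened and delayed. Step 4 shows little effect on markers with a half-life of 24 hours or less. HDL, also in the list, is described in Protocol 4.2 as rising after cessation. Of the markers in this analysis, Total NNAL is the only slow one for which the documents give a half-life.
- A reader might take 93–95% against 12.5–25% as the typical distortion. That is the extreme pair; the even-spread average is 42–54%.
- A reader might infer an effect on the main conclusions. No primary endpoint, test, power figure or type I error depends on this variable.

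The rule is also openly stated as an assumption, and the planned listings of daily use and of biomarkers by subject and visit would let a determined reader recover the timing.

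**Conclusion.** The point holds as a minor one. Followed as written, the rule overstates time since quitting for nearly every quitter: 1–24 or 1–29 actual days are labelled 30, and for quits on Day 6 to 29, 31–54 are labelled 60 and 61–84 are labelled 90. For Total NNAL, the 30-day group would average about 42% to 54% of the pre-quit level, against 12.5% to 25% at a true 30 days.

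That size rests on nominal visit days, evenly spread actual times over 1–29 days, first-order elimination, a steady level before quitting and full abstinence afterwards. The direction of the error does not need the even spread. The reach is one exploratory, descriptive appendix output, conditional on more than 5 subjects quitting.

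**What to change.** In SAP 12.6.3.10:
1. Define quitting: the use-free period required, how lapses count and how missing diary days count.
2. Derive the last day of use from the daily diary, or from the confinement log for quits before discharge on Day 6.
3. Compute actual days from that date to the actual date of each assessment.
4. Plot individual values against actual days.
5. In the table, keep broad bins labelled by their true range (1–30, 31–60, 61–90 days) and show the mean or median actual days in each. This avoids added suppression under the fewer-than-4 rule and resolves the visit-window ambiguity.

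The cost is a short SAP edit, minor programming and a changed format for Figure 15.1.2.29. No new data are needed. The definition of quitting needs the most thought and should be settled before the dates are derived.

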### 12.6.4 Safety Evaluation

Safety variables monitored in this study include: AEs; vital signs (systolic and diastolic blood pressure, pulse rate, respiratory rate); spirometry; ECG data; concomitant medication, clinical chemistry, hematology, urine analysis safety panel, BMI, physical examination, respiratory symptoms (cough assessment).

#### 12.6.4.1 Safety Reporting

The primary analysis of Safety parameters will be conducted on the Safety Population as described in Section 12.1.3 “Descriptive statistics”.

#### 12.6.4.2 Adverse Events

A product emergent AE is defined as an AE that occurs after first product use or that is present prior to first product use and becomes more severe after first product use. All other AEs will not be summarized but provided in listings only.

All AEs occurring from the signing of informed consent will be recorded electronically. However, only product emergent AEs will be summarized. The AE listings will include all AEs captured in the database at any time during the study (including those from subjects who were not in the safety population).

In general, AE summary tables reporting the number of events and the number and percentage of subjects reporting at least one AE will be produced by randomization arm for the Pre-Randomization and Randomized periods, as reported in Section 12.6.4.1 “Safety Reporting”. AE data during the Randomized period will also be presented stratified by Confinement, Ambulatory, and Safety Follow-up.

Ambulatory AE data will also be reported by product use category (see Table 25) defined on product use over the whole ambulatory period. In particular, the general product use categories for THS 2.2 will be used, and the [Predominantly Abstinence] and [Smoking Abstinence] categories will be presented for THS 2.2 Menthol and mCC arm if at least one subject is associated to these categories.

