#### 6.3.3.1 Dual-use

Although subjects are being requested to use solely the product/regimen allocated to them in their respective study arm, it is considered that during the ambulatory period not all subjects randomized to the THS 2.2 Menthol and SA arms might be exclusively using THS 2.2 Menthol or being abstinent at all times during the study. Subjects may concomitantly use THS 2.2 Menthol and CC (dual-use) or smoke some CC in the SA arm.

To assess dual-use of THS 2.2 Menthol and CC, PMI has defined product use categories defined by the percentage of the reported THS 2.2 Menthol Tobacco Sticks consumption during each time period of interest. The percentage use of THS 2.2 Menthol will be calculated by:

$$100 \times \frac{\text{Total number of THS 2.2 Menthol products used}}{\text{Total number of THS 2.2 Menthol products used} + \text{Total number of CC smoked (menthol and/or non-menthol)}}$$

Product use categories are summarized in Table 25, and Figure 2 presents a detailed overview of the definition of the product use categories.

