### **10.3 Safety Population**

Before randomization, the safety population consists of all the subjects who had at least one exposure to THS 2.2 Menthol (including the product test at Admission Day). This also includes any randomized subjects who had no valid safety assessment post-randomization.

After the randomization, the safety population includes all randomized subjects who had at least one valid safety assessment post-randomization. Subjects in the safety populations will be analyzed according to product use categories defined over the whole ambulatory period.

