#### 12.1.1 Stratified Presentation

The following summaries will be produced by randomization arm, stratified by sex (male vs. female) and mCC consumption (10-19 mCC/day vs. >19 mCC/day) for the PP set at period 1 and 4:

- Demographics and Baseline Characteristics
- COHb, and MHBMA, 3-HPMA, S-PMA and total NNAL adjusted for creatinine.
- Product use

Summaries of data by product use categories will be produced for the product use time periods 1 to 4 (see **Table 25**), as appropriate.

Summaries of safety data will be provided stratified by pre-randomization and randomized period (see **Table 25**).

All endpoints will be summarized stratified by time point as appropriate.

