**Table 25: Stratification Labels**

Stratification Factor	Definition
Product preference (which product the subject would prefer to be randomized to).	THSm2.2 (THS 2.2 Menthol) mCC SA NP (No preference)
Sex	Male Female
Daily mCC consumption (per day)	10-19 >19
Safety Time Periods	Pre-Randomization period ([Product trial – Randomization]) Randomized period Confinement ([Day 1-Day 6 confinement] ) Ambulatory ([Day 6 ambulatory-Day 90 Visit]) Safety Follow-up ([Day 90 Visit – End of Study])
Product Use Time Periods	Period 1 ( [Day 1-Day 6 confinement] ) Period 2 ( [Day 6 ambulatory-Day 30 Visit] ) Period 3 ( ]Day 30 Visit-Day 60 Visit] ) Period 4 ( ]Day 60 Visit-Day 90 Visit] )
Product Use Categories for mCC arm	CC Only (Exclusively CC) CC Dual (Use of other products)
Product Use Categories for SA arm	Abstinent Predominantly Abstinent Not Abstinent
General Product Use Categories for THS 2.2 Menthol arm	THS 2.2 [70-100%] Dual ]30-70%[ CC [0-30%]

PP SetDetailed Product use Categories for THS 2.2 Menthol	Primarily THS 2.2 ([95-100]%) Predominantly THS 2.2 ([70-95]%) Dual Mostly THS 2.2 ([60-70]%) Dual Balanced ([40-60]%) Dual Mostly CC ([30-40]%) Predominantly CC ([5-30]%) Primarily CC ([0-5]%)
---	---

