#### 12.1.5 Handling of Dropouts or Missing Data (including outside the limits of quantification)

For laboratory parameters:

- Values below the lower limit of quantification (LLOQ) will be imputed using LLOQ/2. For values above the upper limit of quantification (ULOQ), the ULOQ will be imputed.
- The number of values below LLOQ or above ULOQ will be presented in each summary table. If 50% or more data are below LLOQ or above ULOQ, only the number (%) of value below LLOQ or above ULOQ will be reported in the summaries, together with minimum and maximum of the observed values.
- Missing data at Baseline will not be imputed.

For BoExp:

- A last observation carried forward (LOCF) approach will be implemented to replace all missing data with the last available data for each parameter being assessed.
- For parameters assessed at several timepoints during a visit, the last available data at the timepoint being assessed collected at previous study visit will be used in the analyses. For example, if on Day 5, the evening assessment (20:00-23:00) is missing for COHb, the evening assessment from Day 4 will be used for analysis regardless whether other COHb assessments are available at Day 5.

For daily product use data in safety summaries:

- Product use categories will be defined based on percentage of THS 2.2 Menthol use calculated by averaging non missing consumption data over the entire ambulatory time interval.

For daily product use data in non-safety analyses and summaries:

- If at least 75% of the daily product use assessments over a period are available, with no more than 7-days of consecutive missing data:
  - Product use categories will be defined based on percentage of THS 2.2 use calculated by averaging non missing consumption data over the analysis interval.
  - Compliance to randomized product will be defined based on the available product use data.
- If less than 75% of the daily product use assessments over a period are available, or product use data is missing over a period of more than 7 consecutive days:
  - Product use categories will be defined based on percentage of THS 2.2 use calculated by considering the missing product use data as the CC use reported at Baseline.
  - Compliance to randomized product will be defined by considering the missing product use data as the CC use reported at Baseline.

For MNWS, QSU-brief, and MCEQ questionnaire data:

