15.2.6.6	Summary of Adverse Events by Product Use Category, System Organ Class, Preferred Term and Relationship to Study Product Exposure and Expectedness – Safety Population
15.2.6.7	Summary of Adverse Events Leading to Study Product Discontinuation, Interruption, or Reduction by System Organ Class and Preferred Term – Safety Population
15.2.6.8	Summary of Adverse Events Leading to Study Product Discontinuation, Interruption, or Reduction by Product Use Category, System Organ Class and Preferred Term – Safety Population
15.2.6.9	Summary of Adverse Events Related to Study Procedure by System Organ Class and Preferred Term – Safety Population
15.2.6.10	Summary of Adverse Events by System Organ Class, Preferred Term and Severity – Safety Population
15.2.6.11	Summary of Adverse Events by Product Use Category, System Organ Class, Preferred Term and Severity – Safety Population
LISTINGS	
15.3.6.1	Listing of Adverse Events

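### Ambulatory AEs are tabulated by a product-use category that includes use after the event, so an AE that arose during THS 2.2 Menthol use can be counted under Dual or CC

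*SAP*

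**What the plan says.** SAP section 12.6.4.2 adds a second view to the AE tables by randomization arm: "Ambulatory AE data will also be reported by product use category (see Table 25) defined on product use over the whole ambulatory period". SAP section 10.3 sets the same window for the post-randomization safety population: "Subjects in the safety populations will be analyzed according to product use categories defined over the whole ambulatory period". SAP section 12.1.5 gives the calculation for safety summaries, a percentage of THS use "calculated by averaging non missing consumption data over the entire ambulatory time interval". None of these sections ends the window at AE onset or ties an AE to use at the time it began.

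SAP section 6.3.3.1 describes the measure as "product use categories defined by the percentage of the reported THS 2.2 Menthol Tobacco Sticks consumption during each time period of interest", that is, sticks as a percentage of sticks plus cigarettes. Table 25 gives the three general categories for the THS arm, with cut-offs at 70% and 30%. SAP section 12.1.1 says "Summaries of data by product use categories will be produced for the product use time periods 1 to 4", with a qualifier that leaves room for exceptions, and sections 10.3 and 12.6.4.2 are such an exception.

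Table 15.2.6.8 in SAP section 12.6.4.2.1 is titled "Summary of Adverse Events Leading to Study Product Discontinuation, Interruption, or Reduction by Product Use Category, System Organ Class and Preferred Term". SAP section 13.2 gives the same table number a different title, referring to study discontinuation and actual exposure. Protocol section 12.4.3 says that the safety population is to be analysed by actual exposure.

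**The concern.** The category attached to an AE depends partly on what the subject did after it, and possibly because of it. A THS-arm subject may use only sticks, have an AE, give up the product and return to cigarettes. The later smoking then lowers that subject's whole-period THS percentage. If it falls below 70%, the AE appears under Dual, and below 30% under CC, although every product used up to onset was a stick.

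For such subjects the direction is predictable: AEs that drive people off THS leave the THS row, which flatters it. Table 15.2.6.8 is the most exposed, because stopping or reducing the product can itself change the category by which the event is tabulated. The by-category tables are where a reader would look for safety by exposure. Five of them (15.2.6.2, 15.2.6.4, 15.2.6.6, 15.2.6.8 and 15.2.6.11) are on the list in SAP section 13.2 for the medical safety officer.

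**Working it through.** The plan states no figure for this effect. The one stated number that the check uses is the ambulatory length of 86 days (Protocol section 4.1, SAP section 6.1). It reproduces as 91 − 6 + 1 = 86, counting Day 6 and Day 91.

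Inputs:
- Measure: 100 × sticks / (sticks + cigarettes), SAP section 6.3.3.1.
- Cut-offs: THS at 70% or more, Dual from 30% to below 70%, CC below 30%, SAP Tables 15 and 25.
- Missing diary days are left out of the average, SAP section 12.1.5.
- Subjects who use other products in the ambulatory period are not withdrawn, SAP section 6.1.
- k, the daily cigarette count after the switch divided by the daily stick count before it. This is not in the documents; the assumed range is 0.5 to 1.5.

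Take a subject who uses only THS for t ambulatory days, has the AE, then smokes only cigarettes for the remaining 86 − t days:

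THS share = t / (t + k(86 − t)).

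The share is below 70% when t < 60.2k / (0.3 + 0.7k), and below 30% when t < 25.8k / (0.7 + 0.3k).

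With k = 1 the share is t/86:
- t = 20: 23.3%, CC
- t = 45: 52.3%, Dual
- t = 60: 69.8%, Dual
- t = 61: 70.9%, THS

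Over the assumed range of k:

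| k | Last stop day filed as CC | Last stop day filed as Dual | Stop days that leave the THS row |
|---|---|---|---|
| 0.5 | 15 | 46 | 46/86 = 53.5% |
| 0.75 | 20 | 54 | 54/86 = 62.8% |
| 1.0 | 25 | 60 | 60/86 = 69.8% |
| 1.25 | 29 | 64 | 64/86 = 74.4% |
| 1.5 | 33 | 66 | 66/86 = 76.7% |

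Other patterns:
- Partial switch after day 30 to half sticks and half cigarettes: (30 + 0.5 × 56)/86 = 58/86 = 67.4%, Dual.
- Withdrawal from the study at t = 20: only earlier use counts, so 20/20 = 100%, THS.
- Stopping all products at t = 20: also 100% by the formula. SAP section 12.6.4.2 allows abstinence categories in the THS arm, so the final label is not certain.
- Use up to onset only: t/t = 100% for every t, so the AE always stays under THS.

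Shortening the window to a product-use period does not remove the problem. Taking period 2 as Day 6 to Day 31 (26 days) and k = 1, a stop after 20 days gives 20/26 = 76.9%, THS, but a stop after 10 days gives 10/26 = 38.5%, Dual.

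**The case against.** The strongest reply is that little rests on these tables. The main AE tables are by randomization arm and are also split by confinement, ambulatory period and follow-up. Tables 15.2.6.8 and 15.2.6.14 have arm-based counterparts in 15.2.6.7 and 15.2.6.13. Relatedness is recorded by product, so in Table 15.2.6.6 a THS-related AE in the CC row would still be labelled as THS-related. AE and daily product-use listings are planned, and no AE comparison is inferential. All of this stands, and it limits the point to descriptive tables.

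The reply also disposes of several stronger readings that a reader might infer:
- That every AE which makes a subject give up THS is filed elsewhere. It moves only if cigarettes are resumed early and heavily enough. Discontinuation, interruption or reduction need not involve cigarettes at all, and a pause in all use leaves the percentage unchanged.
- That randomized cigarette smokers are made to look worse. Table 25 defines these THS, Dual and CC rows within the THS arm; the mCC arm has its own categories.
- That Table 15.2.6.14 is distorted to the same degree. Subjects who leave the study add no diary days, so only the gap between onset and withdrawal matters.
- That the expected loss of half the THS arm from the ambulatory per-protocol set measures the problem. That rule is triggered by more than 2 cigarettes in a day or more than 0.5 a day on average. It says nothing about switching after an AE.

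The reply does not change the rule itself: use after the event enters the category, and nothing in the SAP says so to a reader of these tables.

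**Conclusion.** The point holds in a limited form. As written, the SAP can place an AE that arose during THS use in the Dual or CC row of the by-category tables, which does not match the protocol's intention to analyse safety by actual exposure. For a THS-only user who switches fully at an equal daily rate, this happens for a stop within about the first 60 of 86 ambulatory days, or 46 to 66 days over the assumed range of k.

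These limits rest on an immediate and complete switch at a constant rate. The percentages in the table are shares of possible stop days; they equal shares of such AEs only if stop days are evenly spread. The documents support neither condition and do not say how many subjects would follow this course, so no number of displaced AEs can be given.

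Mainly Table 15.2.6.8 is affected, and also 15.2.6.2, 15.2.6.4, 15.2.6.6 and 15.2.6.11. Table 15.2.6.14 is little affected, and the arm-based tables and the primary analysis not at all. This is a worthwhile, inexpensive correction, not a threat to the study's conclusions.

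**What to change.** In SAP sections 10.3, 12.1.5 and 12.6.4.2, classify by use before the event and use a denominator built in the same way. Either of two forms would do:
- (a) Event rates per person-days, with each diary day and each AE assigned to the category calculated from use up to that day.
- (b) The category from the preceding product-use period, applied to all subjects at risk at the start of the period in which the AE began. For period 2, this is the product used in confinement.

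A numerator based on use up to onset should not be paired with a denominator based on full-period categories. A subject who switches mid-period could then be in the THS numerator but the Dual or CC denominator, and the percentages would no longer be proportions of the group shown.

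If the whole-period tables are kept, footnote that the category includes use after the event and refer to the arm-based tables. The two titles of Table 15.2.6.8 should be reconciled at the same time.

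The cost is SAP wording and programming; the daily diary data are already collected. The downside is that a subject can contribute to more than one category. Smaller cells may also fall under the rule in SAP section 12.1.5.1 that suppresses summaries for fewer than 4 subjects.
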